2.4.4.1.2 Model assumption checks

Homogeneity of treatment effect across baseline LDL-C levels:

In order to check the homogeneity of treatment effect versus baseline LDL-C, the following interaction terms will be added in the primary MMRM model:

- Treatment group * baseline calculated LDL-C
- Treatment group * time point * baseline calculated LDL-C

Within the framework of this model with interaction terms, a graph presenting the LS means difference versus placebo at Week 12 and the corresponding 97.5% CI will be provided by baseline LDL-C value.

Analysis of residuals:

The analysis of the residuals of the MMRM will be primarily based on studentized residuals. It will include:

- Normality of studentized residuals, presented graphically using histogram and QQ-plot;
- Plot of studentized residuals versus predicted values;
- Distribution of studentized residuals, presented graphically using boxplots, within each category of the fixed categorical effects of the MMRM:
 - Treatment group (Placebo Q2W, Alirocumab 150 mg Q4W and Alirocumab 150 mg Q2W);
 - Time point (Week 4, Week 8, Week 10, Week 12);
 - Treatment group-by-time point interaction;

- Stratification factor of statin (Yes/No);
- Stratification factor of statin - by - time point interaction.

2.4.4.1.3 *Sensitivity to randomization strata*

In order to assess the robustness of the primary analysis to randomization stratum mistakes (i.e. the stratum recorded in IRT differs from the actual one), the MMRM model will be re-run including the actual stratum as per the eCRF instead of the stratum recorded in IRT.

2.4.4.1.4 *Subgroup analyses*

To assess the homogeneity of the treatment effect across various subgroups, treatment group-by-subgroup factor, time point-by-subgroup factor and treatment group-by time point-by subgroup factor interaction terms and a subgroup factor term will be added in the primary MMRM model. LS means difference versus placebo at Week 12 will be provided, as well as the corresponding SE and 97.5% CI, within each subgroup. The significance level of the treatment group-by-subgroup factor interaction term at Week 12 will be also provided for each factor for descriptive purpose. Forest plots will be provided. In order to handle unbalances between randomization stratification factors levels, population weights will be used as for the primary analysis model.

Only subgroups with a sufficient number of patients in each level and treatment groups will be evaluated.

Subgroups of interest are:

- BMI ($<25 \text{ kg/m}^2$, $\geq 25 \text{ kg/m}^2$);
- Gender (Female, Male);
- Age ($<65 \text{ years}$, $\geq 65 \text{ years}$);
- Stratification factor of statin as per IRT (Yes, No)
- Randomization strata as per IRT (statin, non-statin LMT, diet alone) : for this specific subgroup factor, the MMRM model will include this randomization strata instead of stratification factor of statin as per IRT,
- Randomization strata as per LMT (statin, Ezetimibe, Fibrate, diet alone) : for this specific subgroup factor, the MMRM model will include this randomization strata instead of stratification factor of statin as per IRT,
- heFH population (Yes, No)
- Prior history of MI or ischemic stroke (Yes, No);
- Diabetes status at baseline (Yes, No), which is defined in [Section 2.1](#);
- Chronic kidney disease (CKD) (Yes, No);
- Prior history of side effects caused by statin (Yes, No)

- Baseline calculated LDL-C (<130, \geq 130 to <160, \geq 160 mg/dL) (ie, <3.37, \geq 3.37 to <4.14, \geq 4.14 mmol/L):
For this specific subgroup factor, the MMRM model will include fixed categorical effects for treatment group, stratification factor of statin, baseline LDL-C category, time point, and the interactions treatment group-by-time point, stratification factor of statin-by-time point, baseline calculated LDL-C category-by-time point, treatment group-by-baseline calculated LDL-C category, and treatment group-by-baseline calculated LDL-C category-by-time point;
- Baseline HDL-C (<40 mg/dL (<1.04 mmol/L), \geq 40 mg/dL (\geq 1.04 mmol/L)),
- Baseline fasting TG (<150 mg/dL (<1.7 mmol/L), \geq 150 mg/dL (\geq 1.7 mmol/L) ie, mixed dyslipidemia);
- Baseline Lp(a) (<30, \geq 30 to <50, \geq 50 mg/dL) (ie, <0.3, \geq 0.3 to <0.5, \geq 0.5 g/L));
- Baseline total PCSK9 level (below the median, at or above the median);
- Baseline free PCSK9 level (below the median, at or above the median).

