There was no safety signal in patients who had at least 2 consecutive values of LDL-C <25 or 15 mg/dL (0.65 or 0.39 mmol/L), particularly in regard to neurological or other adverse effects that could potentially be related to low LDL-C (32). The analysis of the safety data with Q2W dosing did not suggest a safety signal as of 31 December 2014.

Overall, the safety profile of the alirocumab Q4W dosing regimen was similar to alirocumab Q2W regimen, except for the frequency and onset of injection site reactions. The reactions tended to occur sooner after the first drug injection, and last longer, in the alirocumab group.

Further details on alirocumab are provided in the Investigator's Brochure.

Rationale for selection of doses / dose regimens in this study:

This study will explore the alirocumab 150 mg Q4W regimen, which represents a potentially viable alternative to a Q2W regimen for some patients.

Statins increases the activity of nuclear translocation of sterol regulatory element-binding protein 2 (SREBP-2), a transcription factor that activates both the LDL-R and PCSK9 genes. It is proposed that a statin-stimulated increased production of PCSK9 may affect the duration of action of alirocumab in the setting of Q4W dosing, because higher rates of PCSK9 production may result in greater target-mediated clearance of the antibody (33). Compared to statins, fibrates and ezetimibe appear to have less effect on PCSK9 levels (34), and a Q4W dosing regimen is expected to maintain sufficient LDL-C lowering throughout the interdosing interval in patients not receiving a statin but receiving these lipid-lowering therapies as well as for alirocumab monotherapy. The addition of a PCSK9 inhibitor to fibrate therapy may achieve beneficial cholesterol lowering along with the other desirable effects of fibrates (e.g., TG reduction) (35).

For patients receiving alirocumab in monotherapy, phase 1 data consistently suggested that the dose of 150 mg given Q4W should also maintain sufficient LDL-C lowering throughout the interdosing interval; similar profile was observed with a background therapy of ezetimibe or fenofibrate, without statin from PKD12910 study.

[REDACTED]

[REDACTED]

[REDACTED]

[REDACTED]

Rationale for protocol design:

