1.3 DETERMINATION OF SAMPLE SIZE

The study is expected to enroll approximately 159 patients.

Two pairwise comparisons will be performed (Alirocumab 150 mg Q4W versus Placebo Q2W and Alirocumab 150 mg Q2W vs. Placebo Q2W). In order to handle multiple comparisons Bonferroni adjustment will be used, i.e., the alpha level for each comparison is 0.025 to obtain an overall study alpha level of 0.05.

[figure not shown]
A sample size of 38 patients in the ITT population (19 in alirocumab group and 19 in placebo group) will have 90% power to detect a difference of 30% in mean percentage change in calculated LDL-C in any pairwise comparison with a 0.025 two-sided significance level and assuming a common standard deviation of 25%.

As a result, the total sample size needed for efficacy will be 57 patients (19 in each of the two alirocumab arms and 19 in the placebo arm).

The sample size is also considered in order to obtain long-term safety data. A sample size of 159 patients (randomization ratio 1: 1: 1, i.e., 53 in Alirocumab 150 mg Q4W, 53 in Alirocumab 150 mg Q2W, and 53 in Placebo Q2W) will allow having long-term open-label safety data. With this sample size, 100 patients are expected to be exposed to alirocumab for a minimum of 12 months providing that the proportion of drop out in the entire study duration (from randomization to Week 64) is 36%, which is obtained using exponential distribution with the same hazard as that of 30% dropout rate within 12 months. Moreover, with 100 patients treated with alirocumab for at least 12 months, AEs with a rate ≥ 0.03 will be detected with 95% probability.

Therefore, 159 patients (53 in Alirocumab 150 mg Q4W, 53 in Alirocumab 150 mg Q2W, and 53 in Placebo Q2W) will be needed to evaluate both efficacy and safety.

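### In the visible SAP text, baseline total and free PCSK9 are examined as modifiers of the LDL-C effect only through a median split, which costs precision and interpretability in an exploratory analysis

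*SAP*

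**What the plan says.** SAP 2.4.4.1.4 (Subgroup analyses) adds a subgroup factor and its interactions with treatment and time point to the primary MMRM. Two of the listed factors are "Baseline total PCSK9 level (below the median, at or above the median") and "Baseline free PCSK9 level (below the median, at or above the median"). For every factor, "The significance level of the treatment group-by-subgroup factor interaction term at Week 12 will be also provided"; the same sentence ends by saying that this is for descriptive purposes.

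SAP 2.1.7 has total and free PCSK9 measured as serum concentrations at Week 0. SAP 2.4.8 summarises them descriptively. No visible text fits either one on its continuous scale as a modifier of the LDL-C effect.

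SAP 2.4.4.1.2 (Model assumption checks) treats baseline LDL-C differently. It adds a treatment-by-baseline term and "Treatment group * time point * baseline calculated LDL-C", then graphs the Week 12 difference from placebo with its 97.5% CI against baseline LDL-C.

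Protocol Section 4 explains why PCSK9 is of interest for Q4W dosing: "higher rates of PCSK9 production may result in greater target-mediated clearance of the antibody".

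**The concern.** PCSK9 is the drug's target, and the protocol's argument about Q4W duration runs through it. The last active Q4W dose in the double-blind period is at Week 8 (Protocol 8.1.2), so Week 12 is the end of a four-week interval, where a dependence on PCSK9 would be expected to show.

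A sample median corresponds to no threshold in the documents, depends on who is enrolled, and puts patients just either side of it in different groups. A two-group comparison gives a less precise estimate of a graded relation and cannot show how the effect changes with level. A real gradient could then be described as consistency across subgroups, when a model of a kind the SAP already plans for LDL-C would have shown more.

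**Working it through.** **Inputs from the documents.** SD 25 percentage points, 53 patients per arm and 1:1:1 allocation (SAP 1.3). For the primary endpoint, "the alpha level for each comparison is 0.025 to obtain an overall study alpha level of 0.05". No alpha, power or interaction size is given for any subgroup factor.

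**The plan's own figure first.** SAP 1.3 says that 19 per arm "will have 90% power to detect a difference of 30% in mean percentage change in calculated LDL-C" "with a 0.025 two-sided significance level". A two-sample t-test with difference 30 and SD 25 at two-sided 0.025 gives 88.9% power at 18 per arm and 90.8% at 19. The 19 reproduces, so 25 is a usable SD.

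**Information kept by a median split.** For a linear effect this is the squared correlation between the modifier X and the indicator of being above its median.

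- Normal X: correlation = φ(0)/0.5 = 0.3989/0.5 = 0.798; squared, 2/π = 0.637. Loss 36.3%. For this interaction 159 patients count as 159 × 0.637 ≈ 101, and the standard error on the same scale is 1/0.798 = 1.25 times as large.
- Uniform X: correlation = 0.125/(0.2887 × 0.5) = 0.866; squared, 0.75. Loss 25%.
- Lognormal X with log-SD 0.2 to 0.5 and an effect linear on the raw scale: loss 38% to 48% (numerical).

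The 36% here has nothing to do with the 36% dropout figure in SAP 1.3.

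**Power, one alirocumab arm versus placebo.** Let d be the assumed difference in slope, in percentage points of LDL-C change per SD of PCSK9. SE = 25 × √(2/53) = 4.856. Power = Φ(d/SE − z) + Φ(−d/SE − z), with z = 1.960 at two-sided 0.05. For the split, d/SE is multiplied by 0.798. Example, d = 10: d/SE = 2.059 gives 54.0%; 2.059 × 0.798 = 1.643 gives 37.6%.

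| d | 0.05: continuous | split | loss | 0.025: continuous | split | loss |
|---|---|---|---|---|---|---|
| 2.5 | 8.1% | 7.0% | 1.1 | 4.5% | 3.8% | 0.7 |
| 5 | 17.7% | 13.0% | 4.7 | 11.3% | 7.9% | 3.4 |
| 7.5 | 33.9% | 23.4% | 10.5 | 24.3% | 15.7% | 8.6 |
| 10 | 54.0% | 37.6% | 16.4 | 42.8% | 27.5% | 15.3 |
| 12.5 | 73.0% | 53.7% | 19.3 | 63.0% | 42.6% | 20.5 |
| 15 | 87.0% | 69.3% | 17.7 | 80.2% | 58.8% | 21.3 |
| 20 | 98.5% | 90.8% | 7.7 | 97.0% | 85.2% | 11.8 |
| 25 | 99.9% | 98.4% | 1.5 | 99.8% | 96.9% | 2.9 |

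(Losses are in points, taken before rounding.)

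Indexed by the power of the continuous test at 0.05, the loss is 5.7 points at 20% power, 15.4 at 50%, 19.2 at 80% and 6.2 at 99%. At 0.025 it is 7.0 at 20%, 21.4 at 70% to 80% and 7.0 at 99%.

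**Checks.** Simulation (6,000 trials per setting, normal modifier, single-visit linear model, 0.05) gave continuous versus split power of 16.3% vs 12.5% (d = 5), 51.0% vs 34.4% (d = 10) and 84.8% vs 64.9% (d = 15). A 2-df test over three arms with both active slopes at 12.5 gives 75.4% vs 54.6%. If the truth is instead a step of ±10 points at the median, the split wins: 46.0% vs 35.9%.

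**The case against.** **The analysis is descriptive.** A reader might infer that the SAP forfeits planned power, or that the efficacy conclusions are weakened. The documents do not support either: no power was planned for this interaction, and it lies outside the testing hierarchy. This objection stands and limits the point to an exploratory improvement.

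**The power figures rest on assumed slopes.** This stands too. A slope of 12.5 means a 50-point spread in effect between −2 and +2 SD of PCSK9, against a whole Week 12 effect of 44.9 points for 150 mg Q4W versus placebo in the earlier study cited in Protocol Section 4. At slopes of 5 to 7.5, continuous power at 0.05 is only 18% to 34%, so either method would usually miss the interaction. The information ratio does not depend on the slope, but it does depend on normality and linearity. The calculation is also a single-visit approximation, not the planned four-visit, covariate-adjusted MMRM.

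**The rationale concerns PCSK9 production under statins, not baseline serum concentration.** Correct: the protocol does not predict a linear relation with baseline level, and effect by statin stratum is already planned. PCSK9 nevertheless varies within strata, and the SAP itself chose baseline level as a subgroup factor.

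**Other continuous factors in 2.4.4.1.4 are categorised, and a prespecified median gives near-equal groups.** True, and this is a reason to keep the split for display. Of these factors, only baseline LDL-C also gets a continuous interaction model in the visible text, and that section is headed as an assumption check, so the precedent is one of method, not an obligation.

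**A reader might infer that the SAP never examines PCSK9 continuously.** That cannot be established. Pharmacodynamic and efficacy text is blacked out in places (for example SAP 2.1.8), and the appendix summarising the analyses is not available. The statement holds for the visible text.

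**Conclusion.** The point holds as a low-cost improvement to an exploratory analysis. In the visible text both PCSK9 markers are examined as effect modifiers only by a median split, although the SAP applies a continuous interaction model with a graph to baseline LDL-C.

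With a roughly normal modifier (or log modifier) and linear modification, the split discards about 36% of the information; the loss is 25% for a uniform modifier and 38% to 48% for the skewed shapes tried. Where the continuous test would have 20% to 80% power, the split costs about 6 to 19 points at two-sided 0.05 and about 7 to 21 at 0.025. These are not properties of the plan: they assume SD 25, 53 evaluable patients per arm and slopes that the documents do not give. A step at the median reverses the comparison.

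**What to change.** Add to SAP 2.4.4.1.4, labelled exploratory and run separately for total and free PCSK9:

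- The primary MMRM plus log baseline PCSK9, its interaction with time point, treatment group * log PCSK9, and treatment group * time point * log PCSK9.
- A rule for values below the quantification limit: LLOQ/2. SAP 2.5.1 sets pharmacokinetic data below the limit to zero, and PCSK9 is described under the pharmacokinetic variables. If that rule applies, the log is undefined. LLOQ/2 is already the SAP's convention for lipids and safety laboratory data.
- A graph of the Week 12 LS-mean difference from placebo with its 97.5% CI over the observed PCSK9 range, as for LDL-C.
- A linearity check with a quadratic or spline term; a two-group display cannot show curvature.
- A repeat with treatment-by-statin and treatment-by-statin-by-time terms, because statins raise PCSK9 (Protocol Section 4) and the two modifiers would otherwise be mixed.
- The median split kept for the forest plot.

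Cost: SAP wording and two core model runs, or four with the statin-adjusted repeats, plus the linearity refits. They can reuse the structure planned for baseline LDL-C and need no new samples, visits or patients. The downside is a linearity assumption on the log scale and a few more exploratory results to report.

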2.4.4.2 Analyses of secondary efficacy endpoints

Method for controlling the overall type-I error rate when testing the key secondary efficacy endpoints is described in [Section 2.4.4.3](#).

For key secondary efficacy endpoints and other secondary efficacy endpoints (described in [Section 2.1.3.2](#)), descriptive summaries and analyses will be performed in the ITT population or mITT population depending on the estimand.

Multiple types of measurements are planned to be analyzed during differing time points in the trial, specifically continuous measurements expected to have a normal distribution (example: percent change in calculated LDL-C), continuous measurements expected to have a non-normal distribution (example: TG), and binary measurements (example: proportion of patients reaching calculated LDL-C <100mg/dL).

2.4.4.2.1 Continuous endpoints anticipated to have a normal distribution

Continuous secondary variables defined in [Section 2.1.3.2](#) anticipated to have a normal distribution (ie, lipids other than TG and Lp[a]) will be analyzed using the same MMRM model as for the primary endpoint with fixed categorical effects of treatment group, stratification factor of statin as per IRT, planned time points up to Week 12, treatment-by-time point interaction and stratification factor of statin-by-time point interaction, as well as the continuous fixed covariates of corresponding baseline value and baseline value-by-time point interaction.

The percentage change in calculated LDL-C from baseline to averaged Week 10 - 12 will be analyzed using an appropriate contrast statement (assigning a weight of 0.5 for the two time points) from the MMRM model.

2.4.4.2.2 *Continuous endpoints anticipated to have a non-normal distribution*

Continuous secondary efficacy variables defined in [Section 2.1.3.2](#) anticipated to have a non-normal distribution (ie, TG and Lp[a]) will be analyzed using multiple imputation approach described below in detail for handling of missing values, followed by the testing of treatment groups using a robust regression model [\(1\)](#). Missing data will be imputed 100 times to generate 100 complete data sets, using the MI SAS procedure. The percent change from baseline at time point of interest will be then derived from observed and imputed lipid values at this time point. The 100 complete data sets will be then analyzed using a robust regression model with endpoint of interest as response variable using M-estimation (using SAS ROBUSTREG procedure) with treatment group, stratification factor of statin as per IRT, and corresponding baseline value(s) as effects. Then the MIANALYZE procedure will be used to generate valid statistical inferences by combining results from the 100 analyses using Rubin's formulae. Combined means estimates for both treatment groups, as well as the differences of these estimates, with their corresponding SEs, 97.5% CIs and p-value will be provided.

Multiple imputation model

Since in general the missing pattern is anticipated to be non-monotone, a two-step approach will be used:

- Step 1: The MCMC (Markov chain Monte Carlo) method will be used in conjunction with the IMPUTE=MONOTONE option to create an imputed data set with a monotone missing pattern;
- Step 2: Using the monotone data set from step 1, missing data will be imputed using the regression method.

Data will be log-transformed before imputation process and then back-transformed to create the imputed data sets using the TRANSFORM statement of SAS MI procedure, since the distribution is assumed non-normal.

Non continuous variables included in the imputer's model (ie, treatment group, randomization strata and gender) are not expected to be missing.

2.4.4.2.3 *Binary endpoints*

Binary secondary efficacy endpoints defined in [Section 2.1.3.2](#) will be analyzed using multiple imputation approach for handling of missing values (see [Section 2.4.4.2.2](#) for details about multiple imputation). In the imputations, log-transform process planned in [Section 2.4.4.2.2](#) will not be done for the lipid parameter assuming normal distribution. The binary endpoint at time point of interest will be derived from observed and imputed lipid values at this time point. Multiple imputation will be followed by stratified logistic regression with treatment group as main effect and corresponding baseline value(s) as covariate, stratified by stratification factor of statin (as per IRT, as defined in [Section 1.4](#)). Combined estimates of odds ratio versus placebo, 97.5% CI, and p-value will be obtained through the SAS MIANALYZE procedure.

In the data dependent case such logistic regression is not applicable (eg, the response rate is zero in 1 treatment arm and thus the maximum likelihood estimate may not exist), the last observation carried forward (LOCF) approach would be used for handling of missing values and a stratified exact conditional logistic regression would be performed to compare treatment effects. The LOCF imputation method for the endpoints at Week12 will consist of using the last value obtained up to the Week 12 analysis window to impute the missing Week 12 value.

In case of computing issues with exact logistic regression, the baseline level(s) will be entered in the model as a categorical variable(s) using quartiles

2.4.4.2.4 *Sensitivity analyses of key secondary endpoints*

2.4.4.2.5 *Analyses of key secondary endpoints by subgroups*

The endpoint “percent change in fasting TG from baseline to Week 12” will be analyzed according to the following subgroups:

Baseline fasting TG (<150 mg/dL (<1.7 mmol/L), \geq 150 mg/dL (\geq 1.7 mmol/L)) ie, mixed dyslipidemia)

2.4.4.2.6 Summary of results per time point

2.4.4.3 Multiplicity issues

The multiplicity appears in two kinds in this study, due to the presence of the 2 arms of alirocumab 150 mg Q4W and 150 mg Q2W that are compared with placebo, and due to the multiple key secondary efficacy endpoints.

The overall type I error will be controlled at 0.05 by performing each pairwise test (alirocumab 150 mg Q4W vs. placebo, and alirocumab 150 mg Q2W vs. placebo) for the main efficacy endpoint at the 0.025 level.

Then, a hierarchical procedure will be used for each pairwise comparison to control the type I error and to handle multiple endpoints. If the primary endpoint analysis is significant at the 2.5% alpha level, the key secondary efficacy endpoints will be tested sequentially at the 0.025 level, using the order defined in [Section 2.1.3.2.1](#). Hierarchical procedure for comparisons of alirocumab 150 mg Q4W versus placebo, and alirocumab 150 mg Q2W versus placebo will be processed separately.

No further adjustments will be made for other secondary endpoints for which p-values will be provided for descriptive purpose only (no claim).

In addition, no further adjustment will be made for multiple analyses (i.e., first and second analyses), since the primary efficacy endpoint and the key secondary efficacy endpoints will all have been conducted at the time of first analysis. [REDACTED]

